4.3 Time and Events Table

	Visit 1 (Screening)	Visit 2 (Procedure)	Visit 3 (1 Day)	Visit 4 (1 week)	Visit 5 (3 month)	Visit 6 (6 Month)	Visit 7 (12 month)
Informed Consent	X						
MRI	X					X	
PAE procedure		X					
IPSS w/QOL	X				X	X	X
Qmax	X				X	X	X
PVR	X				X	X	X
Medication History Questionnaire	X	X			X	X	
AE Assessment			X	X	X	X	

5.0 DEVICE

5.1 Name of Device

HydroPearl® compressible microspheres (75 to 400 μm)

5.2 Intended Use of the Device

HydroPearl® compressible microspheres (75 to 400 μm) will be used for prostatic artery embolization in patients with BPH consistent with labeling.

5.3 Description of the Device

HydroPearl® compressible microspheres are part of a family of embolic materials based on Microvention's proprietary microsphere technology. These spheres are designed to offer controlled, targeted embolization. HydroPearl microspheres are made using Poly-Ethylene Glycol and are precisely calibrated, non-resorbable, hydrophilic, compressible, and biocompatible. HydroPearl® microspheres are available from 75-1100 μm and are provided in a sterile syringe pre-filled with microspheres in phosphate buffered saline.

The HydroPearl® compressible microspheres are intended for the embolization of arteriovenous malformations and hypervascular tumors, including uterine fibroids and benign prostatic hyperplasia.

- HydroPearl® compressible microspheres are contained in a sterile 20 cc pre-filled syringe and packaged in a pre-formed tray with Tyvek peel-away lid.
- Each syringe contains approximately 2 ml of HydroPearl compressible microspheres in non-pyrogenic, sterile, transport solution of physiological buffered saline.
- The product is packaged sterile. Do not use if the unit package is opened or damaged.
- Each syringe is intended for a single patient use only. Do not re-sterilize. Discard any unused material.

Once a catheter has been fluoroscopically guided into the target vessel, the embolization spheres are then injected, causing obstruction at the arteriole level until the desired degree of embolization has occurred. The embolization spheres used during the study will be unchanged.

5.4 Expected Risks

A recent meta-analysis of PAE data from 662 patients in nine studies reported only two major complication (0.3% major complication rate) involving bladder ischemia requiring surgery and severe urinary sepsis requiring hospitalization. Among minor complications transient rectal pain and/or dysuria (9.1%), acute urinary retention (7.9%) and transient hematuria (4.4%) were the most common (1).

Detailed risk analysis is below:

	Risk or Side Effect	Source of Risk or Side Effect	Possible	Less Possible	Rare Events
Potential Risks Associated Study Enrollment & Study Procedures	Discomfort	Blood draw for lab test, ultrasound or MRI	X		
	Thrombophlebitis, bruising, bleeding, blood clot, Pre-syncope or Syncope (i.e. Fainting)	Blood draw for lab tests		X	
	Anxiety or Claustrophobia	MRI scan		X	
	Psychological Discomfort	Clinical Trial			X
	Infection	Blood draw for lab tests			X
	Allergic Reaction	MRI contrast			X
	Gadolinium contrast adverse reaction (i.e. Nephrogenic Systemic Fibrosis or severe skin reaction from contrast agent only reported in patients with kidney dysfunction)	MRI Contrast injection			X
	Confidentiality breach from Medical Records	Medical Record Keeping			X
	Groin/Anesthetic Injection/Neurologic Injury/	Pressure during arterial access and	X		
	Discomfort/Pain	after catheter removed at the leg/femoral artery site	X		
Risks of the PAE	Radiation Exposure Injury	PAE procedure			X
	Kidney Dysfunction	Contrast injected during procedure		X	
	Infection	PAE Procedure		X	

Procedure and Post-operative care	Adverse or Allergic Reaction	Intravenous contrast agent or medications administered as part of procedure or follow-up care (ie. MRI contrast)		X	
	Tissue damage to Skin, Muscle, Skin or other structure in legs and groin (Non-target Embolization)	PAE procedure			X
	Minor Bruising or Bleeding	PAE procedure			X
	Bleeding requiring Transfusion or surgery	PAE procedure			X
	Post Embolization Syndrome, including fever, malaise, headache, and myalgia (body aches)	PAE procedure		X	
	Internal bleeding, such as Gastrointestinal bleeding	Medications taken after the procedure (i.e. Ibuprofen)			X
	Infection	Catheter site in the leg/groin			X
	Arterial injury/trauma, laceration, bruising/pseudo aneurysm	Procedure/ Closure device (clip) on the artery			X
	Pulmonary embolism (clot in lung), Thrombophlebitis (clot in artery or vein)	PAE procedure			X
	Myocardial Infarction (Heart attack)	PAE procedure including moderate sedation/sedative medication			X
	Stroke	PAE procedure including moderate sedation/sedative medication			X

	Disability	PAE procedure including moderate sedation/sedative			X
	Death	PAE procedure including moderate sedation/sedative medication			X

5.5 Risk Minimization

The PAE procedure will be performed by board-certified interventional radiologists who have expertise in endovascular techniques, particularly in selective catheterization and transcatheter embolization techniques. Analgesia during the procedures will be provided through the use of conscious sedation if required. The risks of conscious sedation will be minimized by continuous monitoring of heart rate, blood pressure, oxygen saturation, and cardiac rhythm. The dose area product projected for the procedure is thought to be less than 30 gray/cm² which is about 2-4 years of background radiation and significantly less than that of a cardiac catheterization. Radiation exposure will be minimized to subjects under the principal of 'as low as reasonably achievable' (ALARA).

Sterile instruments with a sterile technique will be used to minimize infection risk at the arterial access site. Pre-operative antibiotic(s) will be administered to reduce risk of other infections, such as urinary tract. The arterial access site discomfort will be minimized by administration of local anesthesia into the overlying skin and adjacent tissues. Catheter access into the appropriate artery may be performed using ultrasound-guided arterial puncture to prevent inadvertent vessel puncture with subsequent bleeding. Real-time fluoroscopic monitoring of all catheter/wire manipulations will be used to prevent vascular injury.

The subject will be monitored for the risk of an allergic response to iodinated contrast. To minimize the risk of renal dysfunction there will be use of non-ionic contrast agents, and appropriate pre-procedure hydration, when necessary. Subjects who report an allergic reaction to iodinated contrast will be pre-medicated as per routine allergy prophylaxis per standard of care.

5.6 Receiving, Storage, Dispensing and Return

5.6.1 Receipt of Supplies

Terumo will provide, at no charge, up to 10 boxes (5 vials/box) of HydroPearl® microspheres for the Study ("Devices"). HydroPearl® microspheres will be stored within the Interventional Radiology Department in a separate area. Embolic devices will be labeled 'for investigational use only' and will be reserved for use in the clinical trial.

5.6.2 Storage

HydroPearl® microspheres must be stored in a cool, dark, dry place in their original packing.

5.6.3 Dispensing

No study specific dispensing techniques will be used.

5.6.4 Return or Destruction of Device

The Institution and Sponsor-Investigator shall, return any such Product to Company promptly if requested by the Company upon the completion or termination of the Study for which such Product was being utilized, or promptly dispose of or destroy, as the Company may reasonably direct, all of its remaining stocks of Product. All Devices supplied by Terumo to Institution for the Study shall be used by Institution only as specified in the Protocol and the Clinical Trial Agreement. No other use of the Devices is authorized.

Disposable syringes, which spherical particulate is stored in, will be discarded as medical waste and packaging will be kept in a secure location until the study is completed. Packages will be disposed of upon completion of the study.

Lot numbers of the device used will be recorded in the CRFs for the study procedure.

6.0 UNANTICIPATED CONCERNS (DEVICES)

6.1 Unanticipated Adverse Device Effect (UADE)

The investigational device exemption (IDE) regulations define an unanticipated adverse device effect (UADE) as “any serious adverse effect on health or safety or any life-threatening problem or death caused by, or associated with, a device, if that effect, problem, or death was not previously identified in nature, severity, or degree of incidence in the investigational plan or application (including a supplementary plan or application), or any other unanticipated serious problem associated with a device that relates to the rights, safety, or welfare of subjects” (21 CFR 812.3(s)).

6.2 Unanticipated Problems (UP)

As defined by UNC’s IRB, unanticipated problems involving risks to study subjects refers to any incident, experience, or outcome that:

- Is unexpected (in terms of nature, severity, or frequency) given (a) the research procedures that are described in the protocol-related documents, such as the IRB-approved research protocol and informed consent document; and (b) the characteristics of the subject population being studied;
- Is related or possibly related to a subject’s participation in the research; and

- Suggests that the research places subjects or others at a greater risk of harm (including physical, psychological, economic, or social harm) related to the research than was previously known or recognized.

6.3 Reporting

6.3.1 UADEs

UADEs must be reported by the clinical investigator to the sponsor and the reviewing IRB, as described below:

For this device study, investigators are required to submit a report of a UADE to the FDA, the manufacturer of the device and the UNC IRB as soon as possible, but in no event later than 10 working days after the investigator first learns of the event (§ 812.150(a)(1)), using the MedWatch Form 3500A. Sponsors must immediately conduct an evaluation of a UADE and must report the results of the evaluation to FDA, the UNC IRB, and participating investigators within 10 working days after the sponsor first receives notice of the effect (§§ 812.46(b), 812.150(b)(1)).

For this device study, we will submit a report of a UADE to the manufacturer and the IRB as soon as possible, but no later than 10 working days after the investigators first learn of the event.

6.3.2 UP

Any events that meet the criteria for “Unanticipated Problems” as defined by UNC’s IRB must be reported by the clinical investigator using the IRB’s web-based reporting system.

Any unanticipated problem that occurs during the conduct of this study and that meets **at least** the first two criteria listed in section 6.2 must be reported to the UNC IRB using the IRB’s web-based reporting system.

7.0 ADVERSE EVENTS (DRUGS- CONTRAST AGENTS)

7.1 Definitions

7.1.1 Adverse Event (AE)

An adverse event (AE) is any untoward medical occurrence (e.g., an abnormal laboratory finding, symptom, or disease temporally associated with the use of a drug) in a patient or clinical investigation subject administered a pharmaceutical product and which does not necessarily have a causal relationship with this treatment. An AE can therefore be any unfavorable and unintended sign (including an abnormal laboratory finding), symptom, or disease temporally associated with the use of a medicinal product, whether or not related to the medicinal product.

Hospitalization for elective surgery or routine clinical procedures that are not the result of an AE (e.g., surgical insertion of central line) need not be considered AEs and should not be recorded as an AE. Disease progression should not be recorded as an AE, unless it is attributable by the investigator to the study therapy.

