4.1.4 Prior and Concomitant Therapy

The subjects will be required to have been on medical therapy for BPH for at least six months prior to undergoing PAE. Such medications include alpha blockers, 5-ARIs or combination therapy. The medication usage will be stopped by the 3 month visit in order to allow an adequate washout period for 5-ARI's prior to the 6 –month visit.

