4.1.10 Visit 5 - 3 Month Follow-Up

Subjects will return 90 +/- 14 days after PAE procedure to complete IPSS, and QOL questionnaires; to have Qmax and PVR measured; medication history questionnaires will be completed; and subjects will be evaluated for possible adverse events. It will be recorded if subjects are unable to hold medications at this time due to residual urinary symptoms. If an AE is suspected based on change in pain scores or functionality, an appropriate work-up will be performed.

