To address the secondary aim, we will tabulate the proportion of patients AEs pre- and post-PAE, comparing the proportion using McNemar's test. A p-value <0.05 for McNemar's test will be considered evidence that the proportion of AE's differs for medication, compared to PAE. A p-value >0.05 will be considered inconclusive. We will assume that the adverse events that occur following PAE will be attributed to the procedure and not medication.

We will present the percentage of prostate infarcted at 6 months and the incidence of minor complications at 1 month descriptively, and calculate 95% confidence intervals. Post-acquisition segmentation software will be used to measure infarct volume.

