9.3 Monitoring/Auditing

9.3.1 Data and Safety Monitoring Plan

Data and Safety Monitoring will be performed by a licensed physician who is not a study investigator.

The CRFs and any relevant source documents will be sent to the Study Monitor (as above) who will review them after treatment is complete for subjects 1, 10, 20 and 30.

Complications will be assessed by the co-PIs, categorized into major and minor categories and recorded on the CRF. CRFs and appropriate source documents will be made available to this individual for annually (every 12 months) review to ensure completeness of data collection. Any discrepancies will be immediately addressed by the co-PIs. All adverse events will be recorded and then summarized for inclusion in the final manuscript. Relatedness to the study

procedure will be assessed by an appropriately delegated investigator based on licensure.

Data monitoring will be performed by Study Monitor listed above. CRFs and appropriate source documents will be made available to this individual for bi-monthly review to ensure completeness of data collection. Any discrepancies will be immediately addressed by the co-PIs.

Because this is a small study with only 30 subjects, no DSMB will be used for this study. Data and safety monitoring will be conducted by an individual (Study Monitor) who is not an investigator on this study (see above).

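### The disease-progression exclusion in Section 7.1.1 permits, but does not require, urinary events after the drug stop to be left out of the AE and SAE data

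*Combined protocol and SAP*

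**What the plan says.** All references are to the combined protocol and SAP.

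- **Recording rule.** Section 7.1.1, which holds the protocol's only AE definition, states: "Disease progression should not be recorded as an AE, unless it is attributable by the investigator to the study therapy". It sits in a section headed for drugs and contrast agents, and the definition speaks of a subject given a pharmaceutical product.
- **Drug stop.** Section 4.1.4: "The medication usage will be stopped by the 3 month visit in order to allow an adequate washout period" for 5-ARIs before the 6-month visit.
- **Failure to stop.** Section 4.1.10: "It will be recorded if subjects are unable to hold medications at this time due to residual urinary symptoms". The section does not say whether this is an AE.
- **Known complication.** Section 5.4 lists acute urinary retention among the minor complications of PAE, at 7.9%.
- **Analysis rule.** Section 8.3 compares the proportion of patients with AEs before and after PAE by McNemar's test, and adds: "We will assume that the adverse events that occur following PAE will be attributed to the procedure and not medication".
- **General statement.** Section 9.3.1: "All adverse events will be recorded and then summarized for inclusion in the final manuscript".
- **Windows and forms.** Sections 7.2 and 7.3.1 run recording from day 1 of study treatment to 30 days after treatment is discontinued. Section 4.3 schedules AE assessment at 1 day, 1 week, 3 months and 6 months. The urinary items on the Section 12.2 form are dysuria and blood in the urine. It has no item for retention or worsening symptoms.

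**The concern.** The trial asks whether PAE can take the place of BPH drugs. If PAE falls short in a given man, the foreseeable harm is worsening obstruction once the drugs are withdrawn: retention, catheterisation, or infection arising from retention. Those are the events that an investigator could most readily call progression of BPH. Under 7.1.1 they then enter the AE data only if the investigator attributes them to the study therapy, a term the protocol does not define and does not extend to the drug stop.

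Two outputs are exposed. One is the pre/post comparison of AE proportions, which serves the secondary aim of showing fewer AEs with PAE than with medication. The other is the SAE count, because Section 7.1.4 defines seriousness only for an event already classed as an AE or SAR. A hospital stay for retention that is classed as progression could drop out of both.

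**Working it through.** This is a recording rule, so the check is mainly a reading of the sections against each other. The plan gives no figure to reproduce.

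**1. Does the attribution exception catch these events?** Not reliably. The section headed Study Treatment (4.1.2) describes the procedure, so PAE is a natural reading of study therapy. The drug stop, however, is placed under prior and concomitant therapy (4.1.4). The causality factors in 7.1.2 refer to study drug exposure and include the normal clinical course of the disease. Section 7.3.1 does name medication washout as a protocol-mandated intervention, but only for SAEs before study medication starts; here the washout follows PAE. An investigator could reasonably judge that symptoms returning after an earlier drug is withdrawn are BPH.

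**2. Does another rule restore them?** The 8.3 attribution rule, the 9.3.1 recording statement and the 7.1.4 seriousness definition all act on events already classed as AEs. None says that progression is to be recorded.

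**3. Does the window reach them?** If treatment means the one-time procedure, the window closes about day 30. The 3-month visit falls at 90 ± 14 days, that is day 76 to 104, so the window closes at least 76 − 30 = 46 days before it. If treatment meant the BPH drugs, stopped at that visit, the window would close between day 76 + 30 = 106 and day 104 + 30 = 134. That is still before the 6-month visit at 180 − 14 = day 166 at the earliest. Either reading conflicts with the AE assessment scheduled at 6 months, and the first also conflicts with the one at 3 months.

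**4. What is captured elsewhere?** IPSS, QoL, PVR and Qmax at 3, 6 and 12 months (4.2.2), inability to hold drugs at 3 months (4.1.10), new or escalated conservative therapy (4.1.13), and complications graded major or minor on the CRF (9.3.1).

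**5. Scale, for illustration only.** The documents give no rate of retention after drug withdrawal.
- *Assumption A:* 3% to 10% of 30 men. 0.03 × 30 = 0.9 and 0.10 × 30 = 3, so about 1 to 3 men.
- *Assumption B:* the 7.9% PAE retention rate from 5.4 is borrowed. 0.079 × 30 = 2.37 expected; P(at least one) = 1 − 0.921^30 = 0.915. With 24 men (20% dropout, from 8.2): 0.079 × 24 = 1.90 expected; P(at least one) = 1 − 0.921^24 = 0.861. These are chances that retention occurs, not that it goes unrecorded.
- *Sensitivity of the test:* exact two-sided McNemar with invented discordant counts (AE before only v after only). For 10 v 2, p = 2 × (1 + 12 + 66)/2^12 = 158/4096 = 0.039. For 10 v 4, p = 2 × (1 + 14 + 91 + 364 + 1001)/2^14 = 2942/16384 = 0.18. Two unrecorded men can move the result across 0.05, but only if neither has any other recorded post-PAE AE.

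**The case against.** A reader might infer that the protocol bars retention from the safety data, hides the main risk of the strategy and so biases the AE comparison towards PAE. The documents do not support that.

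- **The sentence carries an exception.** Retention is a listed PAE complication, so early retention would normally be attributed to the procedure and recorded. Its appearance in 5.4 does not in itself contradict 7.1.1. This stands.
- **Symptom worsening is not hidden.** It is the primary outcome, and keeping symptom scores as effectiveness data is a defensible choice. This stands, and the fix respects it.
- **The heading argument cuts both ways.** If Section 7 covers only drugs and contrast agents, its exclusion may not reach post-PAE events, which have their own routes: the complication record in 9.3.1, device-effect and unanticipated-problem reporting in Section 6, and the stopping rule in 8.1. This stands in part. Those routes serve complications and unanticipated problems; none says how a urinary event after the drug stop is classified.
- **The direction of bias is not established.** The same sentence would exclude progression on drugs before PAE, and Section 4.3 marks no AE assessment at Visits 1 or 2, so the pre-PAE count is itself unclear. On the other side, complete retention is an exclusion criterion (3.2.10), so new complete retention would fall after enrolment. The net direction depends on how investigators classify events.
- **The AE outcome in 2.3.2 is set at 3 months.** Many events after the stop could fall later whatever 7.1.1 says. This stands, and is one more reason to settle the window.

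**Conclusion.** The concern holds in a limited form. As written, 7.1.1 lets an unblinded investigator class retention or another urinary event after the required drug stop as BPH progression and leave it out of the AE and SAE data, and no other section corrects this. It permits omission and does not direct it. The likely loss is small: at most a few men on the illustrative rates, and fewer in the McNemar comparison, where a man counts only once. The actual size cannot be derived from the documents. A bias towards PAE would arise only if investigators used the exclusion mainly for post-PAE events in men with no other recorded AE. The IPSS analysis is not affected. The rule should still be changed, because it leaves part of a safety comparison to case-by-case discretion and the remedy is cheap.

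**What to change.** These changes concern recording only, not clinical management.

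1. In 7.1.1, limit the progression exclusion to change in IPSS or symptom score alone.
2. State that acute retention, catheterisation, urinary infection, and any hospital or emergency visit for urinary symptoms after PAE are recorded as an AE or SAE whatever the cause, with relatedness to PAE, the drug stop or underlying BPH noted.
3. Add these items to the Section 12.2 AE form.
4. Reconcile the 30-day window in 7.2 and 7.3.1 with the AE assessments at 3 and 6 months, saying what treatment discontinuation means for a one-time procedure.

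The cost is a short amendment to Section 7 and a few more CRF fields. The downside is a slightly higher recorded AE rate after PAE. Recording relatedness lets the report show how much of that is due to the procedure, the drug stop or the disease.

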7.1.2 Suspected Adverse Reaction (SAR)

A suspected adverse reaction (SAR) is any AE for which there is a *reasonable possibility* that the drug is the cause. *Reasonable possibility* means that there is evidence to suggest a causal relationship between the drug and the AE. A suspected adverse reaction implies a lesser degree of certainty about causality than adverse reaction, which means any adverse event caused by a drug.

Causality assessment to a study drug is a medical judgment made in consideration of the following factors: temporal relationship of the AE to study drug exposure, known mechanism of action or side effect profile of study treatment, other recent or concomitant drug exposures, normal clinical course of the disease under investigation, and any other underlying or concurrent medical conditions. Other factors to consider in considering drug as the cause of the AE:

- Single occurrence of an uncommon event known to be strongly associated with drug exposure (e.g., angioedema, hepatic injury, Stevens-Johnson Syndrome)
- One or more occurrences of an event not commonly associated with drug exposure, but otherwise uncommon in the population (e.g., tendon rupture); often more than once occurrence from one or multiple studies would be needed before the sponsor could determine that there is *reasonable possibility* that the drug caused the event.
- An aggregate analysis of specific events observed in a clinical trial that indicates the events occur more frequently in the drug treatment group than in a concurrent or historical control group

